7.3 Tables for Comparison of Patient and Clinician data

For tables comparing patient and clinician data, the FAS dataset is used for analysis only in the instances patient data has corresponding clinician week 12 data. All data tables in this section pertain to FAS population.

Table 3.1 Overall Appearance in Original Treatment Area: Patient and Clinician

7.1.10 & 7.2.13

Question	Statistics	Week 8		Week 24	
		PER1 Patient (N=x)	AK8_2 Clinician (N=x)	PER24_1 Patient (N=x)	AK8_2 Clinician (N=x)
Compared to [8 or 24] weeks ago (at the beginning of the study), how has the overall appearance of the skin in the original AK treated area changed? 1. Much Worse 2. Somewhat Worse 3. No Change 4. Somewhat Improved 5. Much Improved (1 / 2) Much / Somewhat Worse (3) No Change (4 / 5) Somewhat / Much Improved	Mean (SD), Median, Min, Max n (%) n (%) n (%) n (%) n (%) n (%) n (%) n (%)				

Table 3.2 Treatment Satisfaction Questionnaire for Medication Scores in the Original Treatment Area: Patient and Clinician

7.1.12 & 7.2.15

Domain	Statistics	Week 8 Patient (N=x)	Week 8 Clinician (N=x)	Week 24 Patient (N=x)	Week 24 Clinician (N=x)
Effectiveness	Mean (SD) Median Min, Max				
Convenience	Mean (SD) Median Min, Max				
Global Satisfaction	Mean (SD) Median Min, Max				

Table 3.3 Satisfaction with Tirbanibulin in the Original Treated Area (looks/texture): Patient and Clinician
7.1.14 & 7.2.17

Questions	Statistics	Week 8		Week 24	
		Patient (N=x)	Clinician (N=x)	Patient (N=x)	Clinician (N=x)

How satisfied are you with this treatment's ability to improve how your skin looks (example: reduced redness, discoloration, crusting, scaling) in the original AK treated area?
 
1. Extremely Dissatisfied 2. Very Dissatisfied 3. Dissatisfied 4. Somewhat Satisfied 5. Satisfied 6. Very Satisfied 7. Extremely Satisfied
 
(1 / 2) Extremely/Very Dissatisfied (3 / 4 / 5) Dissatisfied/Somewhat Satisfied/Satisfied (6 / 7) Very/Extremely Satisfied
	
Mean (SD), Median, Min,Max
 
n (%)
	PT1	EP1	PT1	EP1

How satisfied are you with this treatment's ability to improve your skin texture (i.e., how your skin feels in terms of roughness, bumpiness, scaliness) as a result of the treatment, in the original AK treated area?	Mean (SD), Median, Min,Max	PT2	EPQ2	PT2	EPQ2
		n (%)	n (%)	n (%)	n (%)
1. Extremely Dissatisfied		n (%)			
2. Very Dissatisfied		n (%)			
3. Dissatisfied		n (%)			
4. Somewhat Satisfied		n (%)			
5. Satisfied		n (%)			
6. Very Satisfied		n (%)			
7. Extremely Satisfied		n (%)			
(1 / 2) Extremely/Very Dissatisfied		n (%)			
(3 / 4 / 5) Dissatisfied/Somewhat Satisfied/Satisfied		n (%)			
(6 / 7) Very/Extremely Satisfied		n (%)			

Table 3.4 Relative Satisfaction of Tirbanibulin in Comparison with Other Topical Medications for AK in the Original Treated Area: Patient and Clinician

7.1.17 & 7.2.20

Domain	Statistics	Week 8 Patient (N=x)	Week 8 Clinician (N=x)
Compared to your [patient's] previous experience with topical treatment X for AK, how would you rate the duration of skin reactions (i.e., how long the skin reactions lasted) associated with tirbanibulin (Klisyri®) in the original AK treated area?	
Mean (SD), Median,Min,Max
 
n (%) n (%) n (%) n (%) n (%)
 
n (%) n (%) n (%)
	TT1	EPQ3
1. Duration of skin reactions was much shorter with tirbanibulin 2. Duration of skin reactions was somewhat shorter with tirbanibulin 3. Duration of skin reactions was the same with tirbanibulin 4. Duration of skin reactions was somewhat longer with tirbanibulin 5. Duration of skin reactions was much longer with tirbanibulin (1 / 2) Duration of skin reactions was much / somewhat shorter with tirbanibulin (3) Duration of skin reactions was the same with tirbanibulin (4 / 5) Duration of skin reactions was somewhat / much longer with tirbanibulin			
Compared to your [patient's] previous experience with topical treatment X for AK, how would you rate the severity of skin reactions (i.e., how bad the skin reactions were) associated with tirbanibulin (Klisyri®) in the original AK treated area?	
Mean (SD), Median,Min,Max
 
n (%)
	TT2	EP4
1. Severity of skin reactions was much better with tirbanibulin			

2. Severity of skin reactions was somewhat better with tirbanibulin 3. Severity of skin reactions was the same with tirbanibulin 4. Severity of skin reactions was somewhat worse with tirbanibulin 5. Severity of skin reactions was much worse with tirbanibulin
	
n (%) n (%) n (%) n (%) n (%)
	

(1 / 2) Severity of skin reactions was much / somewhat better with tirbanibulin (3) Severity of skin reactions was the same with tirbanibulin (4 / 5) Severity of skin reactions was much / somewhat worse with tirbanibulin
	
n (%) n (%) n (%)
	

Compared to your [patient's] previous experience with treatment X, how would you rate the impact on your daily activities (such as shopping, bathing, social engagements, scheduling vacations, outdoor activities, activities at work, attendance at work, etc.) due to skin reactions associated with tirbanibulin (Klisyri®) use in the original AK treated area?
	
Mean (SD), Median,Min,Max
	
TT3 EP5

6. Much better with tirbanibulin 7. Somewhat better with tirbanibulin 8. Same with tirbanibulin 9. Somewhat worse with tirbanibulin 10. Much worse with tirbanibulin
 
(1 / 2) Much / somewhat better with tirbanibulin (3) Same with tirbanibulin (4 / 5) Somewhat / much worse with tirbanibulin
	
n (%) n (%) n (%) n (%) n (%) n (%) n (%) n (%)
	

Compared to your [patient's] previous experience with topical treatment X for AK, how would you rate the convenience / ease of use (such as frequency of use, easy to follow instructions, comfortable to apply, etc.) associated with tirbanibulin (Klisyri®)
	
Mean (SD), Median,Min,Max
	
TT4 EP6

treatment?
 
6. Ease of use & convenience was much better with tirbanibulin
 
7. Ease of use & convenience was somewhat better with tirbanibulin
 
8. Ease of use & convenience was the same with tirbanibulin
 
9. Ease of use & convenience was somewhat worse with tirbanibulin
 
10. Ease of use & convenience was much worse with tirbanibulin
	
n (%)
 
n (%)
 
n (%)
 
n (%)
 
n (%)
	

(1 / 2) Ease of use & convenience was much / somewhat better with tirbanibulin
	
n (%)
	

(3) Ease of use & convenience was the same with tirbanibulin
	
n (%)
	

(4 / 5) Ease of use & convenience was somewhat / much worse with tirbanibulin
	
n (%)
	

Compared to your [patient's] previous experience with topical treatment X for AK, how would you rate your overall satisfaction (considering the factors such as convenience/ ease of use, duration and severity of skin reactions, impact on daily life, etc.) with tirbanibulin (Klisyri®) treatment?
	
Mean (SD), Median,Min,Max
	
TT5

6. My satisfaction is much better with tirbanibulin
	
n (%)
	

7. My satisfaction is somewhat better with tirbanibulin
	
n (%)
	

8. My satisfaction is same with tirbanibulin
	
n (%)
	

9. My satisfaction is somewhat worse with tirbanibulin
	
n (%)
	

10. My satisfaction is much worse with tirbanibulin
	
n (%)
	

(1 / 2) My satisfaction is much / somewhat better with tirbanibulin
	
n (%)
	

(3) My satisfaction is same with tirbanibulin
	
n (%)
	

(4 / 5) My satisfaction is somewhat / much worse with tirbanibulin
	
n (%)
	

Table 3.5 Tirbanibulin Retreatment Likelihood: Patient and Clinician

7.1.26 & 7.2.33

Domain	Statistics	Week 8 Patient (N=x)	Week 8 Clinician (N=x)	Week 24 Patient (N=x)	Week 24 Clinician (N=x)

PT3: In case you need to be retreated for AK, how likely are you to consider tirbanibulin (Klisyri®) again?
 
Very Unlikely Somewhat Unlikely Neutral Somewhat Likely Very Likely
 
Very / Somewhat Unlikely Neutral Somewhat / Very Likely
	
Mean (SD), Median, Min,Max
 
n (%)
				

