3 STUDY DESIGN

This will be a single-arm multi-center prospective cohort study which will enroll adult patients with AK of the face or scalp who are newly initiated with tirbanibulin (Klisyri®) treatment in real-world community practices in the U.S, as part of usual care. Study subjects will be followed for up to 24 weeks post-index date (with the ‘index-date’ defined as the date of initiation of tirbanibulin). Study Site Investigators and subjects will complete electronic data collection forms (e-DCFs, or surveys) at baseline (at time of study enrollment), Week 8 and Week 24.

This study will entail provision of tirbanibulin treatment to study participants. Site Investigators will decide on who to prescribe tirbanibulin (Klisyri®) ointment (as per U.S label) as part of usual care, based on their best clinical judgment, prior to subject recruitment. The study is sponsored by Almirall, hereinafter referred to as the Sponsor. The study will be managed by Avant Health, hereinafter referred to as the Contract Research Organization (CRO).

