4 STUDY SCHEDULE & PROCEDURES

Study eligible patients who are considered as candidates for tirbanibulin treatment as part of usual care AK management will be screened, consented, and recruited into the study, followed for up to 24 weeks post-index date, encompassing three distinct data collection encounters. With 'T' being the index date of tirbanibulin treatment initiation, the baseline data collection (from both Site Investigators and Subjects) may transpire anytime between T= -2 weeks post-index date and T= +7 days post-index date; the 8-week follow-up data collection (Study Encounter # 2; from both Site Investigators and Subjects) will happen at T=8 weeks post-index date \pm 7 days; and 24-week follow-up data collection (Study Encounter #3; from both Site Investigators and Subjects) will happen at T=24 weeks post-index date \pm 14 days. Index date is the planned date of first application/initiation of tirbanibulin treatment, after the subject was prescribed the tirbanibulin. Different data elements will be collected from Site Investigators and from study Subjects at these data collection encounters, as outlined below.

The schedule of events is summarized in Appendix A.

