5.3.5 Study Subject Photographic Assessments

Site Investigators from a subset of study sites (up to 2) will take photographs of AK lesions in Subject’s treatment area on the face or scalp at baseline encounter and at Weeks 1, 2, 4 and 8, during the in-person visits. This photographic data will be used to document and depict the changes in AK lesions and LSRs that may be associated with tirbanibulin treatment in the study.

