6.3 General Statistical Procedures

6.3.1 Overview

Data from Site Investigators and study Subjects will be combined into one dataset. No site-specific analyses will be conducted. Validated instruments will be scored according to developer guidelines, reporting domain scores and overall summary scores, as appropriate. EPQ and other ad hoc questions will be analyzed and reported individually, based on the respective response scales. For all outcome measures, the analyses will focus on baseline, Week-8 and Week-24, as applicable.

All statistical analyses will be based on all available data assuming that all missing data are uninformative and will be conducted using appropriate statistical software, such as SAS. An interim analysis will be conducted after the completion of 8 weeks of data collection for all study Subjects. The final study analyses will be conducted after the completion of 24 weeks of data collection for all study Subjects.

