7.2 Tables from Clinician's DCF (FAS Population)

Clinician data is analyzed using the FAS dataset. In relevant instances (such as IGA and physician satisfaction evaluations), only FAS dataset with corresponding week clinician data is used. All data tables in this section correspond to FAS population.

Table 2.1 Site Characteristics

Domain	(N=x)
SC1: Current workplace	
Private, office-based practice	n (%)
Hospital-based practice	n (%)
SC2: Total number of board-certified dermatologists in the practice (including yourself, if applicable)	N, Mean (SD), Median, Min, Max
SC3: At present, how many patients with AKs do you personally manage in a given month?	N, Mean (SD), Median, Min, Max
SC4: How long have you been practicing dermatology, post-residency?	N, Mean (SD), Median, Min, Max

Note: Data from Clinician DCF. The denominator for the percentage is N which refers to total number of unique sites in PROSES study.

Table 2.2 Study Subject Selection Criteria

Domain (N=X)	Yes	No
SS1r1 Diagnosed with actinic keratosis of the face and/or scalp?	n (%)	n (%)
SS1r2 Has clinically typical, visible, and discrete AK lesions?	n (%)	n (%)
SS1r3 Considered a candidate for tirbanibulin (Klisyri®) AND you plan to administer tirbanibulin (Klisyri®) treatment?	n (%)	n (%)
SS1r4 At least 18 years of age at the time of initiation of tirbanibulin (Klisyri®) treatment?	n (%)	n (%)
SS1r5 Willing to avoid excessive sun or UV exposure, and/or use relevant sunscreen protection and protective clothing during the study duration.	n (%)	n (%)
SS1r6 Able to read and write English.	n (%)	n (%)
SS1r7 Able to provide consent to participate AND is willing to comply with study procedure?	n (%)	n (%)
SS2r1 Have another dermatological condition of the face that could interfere with the actinic keratosis clinical evaluations?	n (%)	n (%)
SS2r2 Hypertrophic AK lesions, open wounds or suspected skin cancers within close proximity of the treatment area	n (%)	n (%)
SS2r3 Anticipated need for in-patient hospitalization or in-patient surgery within the next 2 months.	n (%)	n (%)
SS2r4 Have a medical chart accessible to complete baseline data collection?	n (%)	n (%)

Note: Data from Clinician DCF. The denominator for the percentage is the number of patients with available data (N=X). There are no missing data.

Table 2.3 Patient Clinical Characteristics from Medical Chart

Character	Statistics	Baseline (N=XX)
PC1 Gender		
Male	n (%)	
Female	n (%)	
Other	n (%)	
PC2 Primary Health Insurance		

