4. Somewhat Satisfied	n (%)	n (%)
5. Satisfied	n (%)	n (%)
6. Very Satisfied	n (%)	n (%)
7. Extremely Satisfied	n (%)	n (%)
8. Don't know / not applicable	n (%)	n (%)
(1 / 2) Extremely/Very Dissatisfied		
(3 / 4 / 5) Dissatisfied/Somewhat Satisfied/Satisfied	n (%)	n (%)
(6 / 7) Very/Extremely Satisfied	n (%)	n (%)
EPQ2: How satisfied are you with this treatment's ability to improve your patient's skin texture (i.e., how the skin feels in terms of roughness, bumpiness, scaliness) as a result of the treatment, in the original AK treated area?	Mean (SD), Median, Min,Max	Mean (SD), Median, Min,Max
1. Extremely Dissatisfied	n (%)	n (%)
2. Very Dissatisfied	n (%)	n (%)
3. Dissatisfied	n (%)	n (%)
4. Somewhat Satisfied	n (%)	n (%)
5. Satisfied	n (%)	n (%)
6. Very Satisfied	n (%)	n (%)
7. Extremely Satisfied	n (%)	n (%)
8. Don't know / not applicable	n (%)	n (%)
(1 / 2) Extremely/Very Dissatisfied	n (%)	n (%)
(3 / 4 / 5) Dissatisfied/Somewhat Satisfied/Satisfied	n (%)	n (%)
(6 / 7) Very/Extremely Satisfied	n (%)	n (%)

Table 2.18 Subgroup Analysis of Clinician Satisfaction with Treatment Ability to Improve How Skin Looks in the Original Treated Area

% Extremely/Very Satisfied		Week 8 n (%)	Week 24 n (%)
Subgroups			
Gender			
Male			
Female			
p -value			
Age Group			
≤ 49 years			
50 – 64 Years			
≥ 65 years			
p -value			
AK Treatment Location			
Face			
Scalp			
Both			
p -value			
Fitzpatrick Skin Type			
I / II			
III / IV / V / VI			
p -value			
Skin Photodamage			
Absent/mild			
Moderate/Severe			
p -value			
History of Skin Cancer			
Yes			
No			
p -value			
Prior Treatment Experience: Use of Cryosurgery			
Yes			
No			
p -value			
Prior Treatment Experience: Use of Other Topical Treatments			

Yes		
No		
p -value		
Prior Treatment Experience: Treatment Naïve at Baseline		
Yes		
No		
p -value		

P-values correspond to difference between strata within respective time periods.

Table 2.19 Subgroup Analysis of Patient Satisfaction with Treatment Ability to Improve Skin Texture in the Original Treated Area

% Extremely/Very Satisfied	Week 8 n (%)	Week 24 n (%)
Subgroups		
Gender		
Male		
Female		
p -value		
Age Group		
≤ 49 years		
50 – 64 Years		
≥ 65 years		
p -value		
AK Treatment Location		
Face		
Scalp		
Both		
p -value		
Fitzpatrick Skin Type		
I / II		
III / IV / V / VI		
p -value		
Skin Photodamage		
Absent/mild		
Moderate/Severe		
p -value		

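### SAP 7.3 admits patients to the patient-versus-clinician tables on Week 12 clinician data, which this study does not collect; the rule needs to be same-week pairing.

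*SAP*

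**What the plan says.** The opening sentence of SAP 7.3 states the inclusion rule for the tables that compare patient and clinician answers: "the FAS dataset is used for analysis only in the instances patient data has corresponding clinician week 12 data".

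The rest of the SAP describes a different schedule. Section 3 has Site Investigators and subjects completing forms "at baseline (at time of study enrollment), Week 8 and Week 24". Section 4 describes follow-up as "encompassing three distinct data collection encounters". Section 6.3.1 states: "For all outcome measures, the analyses will focus on baseline, Week-8 and Week-24, as applicable". The only additional visits are at the photography sites (SAP 5.3.5), where pictures are taken "at baseline encounter and at Weeks 1, 2, 4 and 8".

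SAP 7.2, which covers the clinician tables, words its own restriction without a fixed week. For measures such as the IGA and clinician satisfaction, "only FAS dataset with corresponding week clinician data is used".

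Table 2.17 (clinician satisfaction with skin looks and texture) lists a further response, "8. Don't know / not applicable". Table 3.3 places the same items beside the patients' answers and has no row for that response.

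**The concern.** The sentence in 7.3 is an operative inclusion rule: it decides who is counted in five tables. It names a visit that does not exist, so a programmer has to substitute something, and the possible substitutes do not give the same tables.

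It is also the only text that matches patients to clinicians in these tables. Under SAP 7, FAS membership rests on the patient's Week 8 survey. That guarantees neither a clinician form at Week 8 nor any form at Week 24. Table 4.11 counts missing patient surveys and missing clinician surveys separately at each visit, so the plan itself allows for the two to differ.

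If the two columns for a given week hold different patients, a gap between them can reflect who was rated as well as how they were rated. That would weaken a layout whose purpose is to show the two views side by side.

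**Working it through.** No sample size, power or error-rate figure is involved, and the plan gives no number here to reproduce. The check compares the rule with the schedule and the table shells.

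**1. Can any scheduled form count as Week 12 data?** The windows come from SAP Appendix A.

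- Week 8 ± 7 days: 56 − 7 = 49 to 56 + 7 = 63, so days 49 to 63.
- Week 24 ± 14 days: 168 − 14 = 154 to 168 + 14 = 182, so days 154 to 182.
- Week 12: 12 × 7 = day 84.
- Day 84 is 84 − 63 = 21 days after the Week 8 window closes and 154 − 84 = 70 days before the Week 24 window opens.

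No scheduled form qualifies. The photography visits end at Week 8. An early termination encounter could fall near day 84, but Protocol 7.6 has it use the assessments of the next scheduled encounter, so it does not create a Week 12 form.

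**2. Which weeks do the tables show?**

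| Table | Week 8 columns | Week 24 columns | Week 12 columns |
|---|---|---|---|
| 3.1 Overall appearance | yes | yes | no |
| 3.2 Treatment satisfaction scores | yes | yes | no |
| 3.3 Looks and texture | yes | yes | no |
| 3.4 Comparison with other topicals | yes | no | no |
| 3.5 Likelihood of retreatment | yes | yes | no |

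**3. What would each substitute do?**

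- *Week 8 in place of 12.* The Week 8 columns are paired. In the four tables with Week 24 columns, a patient with both Week 8 forms but only one Week 24 form appears in one Week 24 column and not in the other.
- *Week 24 in place of 12.* The Week 24 columns are restricted to patients with a clinician form of that week. A patient can enter the Week 8 patient column without a Week 8 clinician form, and Table 3.4, which shows Week 8 only, would be filtered on a visit it does not report.
- *Same week, as in SAP 7.2.* Each week's pair of columns holds the patients with both forms of that week. Each N is at most the FAS size, so at most about 300. The documents do not give the actual counts.

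Only the third option pairs every column.

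**4. Item level.** The extra response in Table 2.17 is documented for the two clinician items that feed Table 3.3. SAP 5 offers a don't-know option for pertinent measures without listing them. Where a clinician chooses it, both forms exist but there is only one usable rating, and 7.3 does not say whether that patient stays in. This is secondary to the week error.

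**The case against.** The strongest reply is that this is a wrong week number whose intended meaning is clear. The shells have no Week 12 column. The sentence already requires clinician data corresponding to the patient's, and SAP 7.2 uses same-week wording. The SAP also names another study (note to Table 2.1), another drug (7.4) and acne medication (Tables 2.31 and 4.9), so the week may be carried over from another plan, although that origin is an inference. Much of this stands: same-week pairing is the likely intent. But 7.2 does not formally govern 7.3, and the explicit rule in 7.3 contradicts the schedule, so the choice would still be made outside the plan.

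Two stronger readings are tempting and should be set aside. A reader might infer that all five tables will be empty. That is the literal result of the rule, but with these shells nobody would deliver empty tables. A reader might also try to put a size on the bias. Suppose 15% of patients lack one of the two Week 24 forms and differ by 20 points from the rest. If all of them sit in one column, the gap shifts by 0.15 × 0.20 = 0.03, or 3 points. If the missing forms split evenly between patient and clinician, and both groups differ in the same direction, each column moves by 7.5/92.5 × 20 ≈ 1.6 points and the gap moves by about 0. Neither the 15% nor the 20 points is in the documents, so no figure can be defended.

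It is also fair to say that patient-clinician disagreement is not a stated objective or endpoint. The additional endpoints report the two sets of ratings respectively, and the 7.3 shells contain no difference, test or agreement statistic. Each column carries its own N, so unequal denominators would be visible.

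**Conclusion.** The inclusion rule in SAP 7.3 is wrong as written and cannot be applied, and no single-week replacement pairs all the columns it governs. This follows directly from the schedule and the shells and needs no assumption.

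The consequence is small. It is confined to descriptive comparisons in Tables 3.1 to 3.5. The separate patient results (Tables 1.10, 1.12, 1.14, 1.17, 1.26) and clinician results (Tables 2.13, 2.15, 2.17, 2.20, 2.33) do not depend on this sentence, nor do the primary Skindex-16 and secondary IGA analyses. The realistic risk is an undocumented programming choice that leaves one week's columns unmatched. It is worth correcting because the correction is cheap, not because any result is shown to be biased.

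**What to change.** Replace the sentence in SAP 7.3 with a same-week rule consistent with SAP 7.2, for example: *At each time point (Week 8, Week 24) separately, Tables 3.1 to 3.5 include FAS subjects with both a patient and a clinician response at that same time point. Where a don't-know or not-applicable option exists (for example the Table 2.17 items shown in Table 3.3), that answer counts as no response. The number of pairs is printed in the column heads.*

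The cost is one sentence in the SAP and one filter in the program. Some columns will have a slightly smaller N than in the separate patient and clinician tables, and a footnote can say why.
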